5.7	Treatment Compliance.....	32
6	STUDY ASSESSMENTS AND PROCEDURES	33
6.1	Study Schematic	Error! Bookmark not defined.
6.2	Time and Events Schedule....	Error! Bookmark not defined.
6.3	Study Materials.....	40
6.4	Safety Assessments	40
7	ADVERSE EVENT REPORTING.....	40
7.1	Adverse Events	40
7.1.1	Serious Adverse Events	41
7.1.2	Nonserious Adverse Events.....	42
7.1.3	Adverse Events of Special Interest.....	42
7.2	Collection and Reporting.....	43
7.2.1	Serious Adverse Event Collecting and Reporting	43
7.2.2	Non-Serious Adverse Events (SAEs) Collecting and Reporting	44
7.3	Laboratory Test Abnormalities	45
7.4	Overdose	45
7.5	Pregnancy.....	45
7.6	Potential Drug-Induced Liver Injury (DILI).....	46
7.7	Other Safety Considerations	46
8	DATA MONITORING COMMITTEE.....	46
9	STATISTICAL CONSIDERATIONS.....	47
10	STUDY MANAGEMENT	49

10.1	Compliance with the Protocol	49
10.1.1	Compliance with the Protocol and Protocol Revisions	49
10.2	Records Retention	50
10.2.1	Records Retention	50
10.2.2	Study Drug Records.....	50
10.3	Destruction of Investigational Product....	Error! Bookmark not defined.
11	GLOSSARY OF TERMS.....	52
12	LIST OF ABBREVIATIONS	53
13	REFERENCES.....	54

PROTOCOL SYNOPSIS

Protocol Title:	Effect of Saxagliptin (DPP-4 Inhibitor) on Endothelial Progenitor Cells (EPCs) as a cellular biomarker for evaluating Endothelial Dysfunction in Early Type 2 Diabetes patients
Site Numbers & Names:	GWU Medical Faculty Associates
Research Hypothesis:	We believe poor viability and function of EPCs in early diabetes ultimately affects the repair and regeneration of the endothelium and that prompts intervention using Saxagliptin with another oral hypoglycemic agent, Metformin, may reduce or reverse cardiovascular risk by improving EPC survival and function above and beyond adequate glucose metabolism control.
Study Schema: Drugs / Doses / Length of Treatment)	We propose a 2-arm randomized, parallel group, longitudinal study of 12-week intervention duration. The 12-week time interval has been previously shown adequate to observe changes in biochemistry, EPCs and, importantly, pulse wave velocity (PWV) changes. Patients will be randomized to 2 groups: Control, (n=20), Metformin + Lifestyle + Placebo. Treatment, (n=20) Metformin+ Lifestyle+ Saxagliptin 5mg.


Study Objectives:
 
 • Primary: • Secondary: 	
The primary objective is to ascertain if addition of Saxagliptin improves endothelial dysfunction in early type 2 diabetes patients.
 
The secondary objective is to establish CD34+ cell number, function and gene expression as important bio-markers to monitor endothelial function.

Study Design:
	
Prospective, double-masked, randomized placebo-controlled trial

Accrual Goal: (Total number of subjects)	N=42
Accrual Rate: (Number of subjects expected per month)	Recruit 42 patients in approximately 36 months.
Estimated: FPFV: LPFV: Follow Up: (dd-mm-yy)	FPFV: 01-10-12. LPFV: 01-06-15
Correlative Studies: (PK/PD, etc.)	N/A
Inclusion Criteria:	
 1. Adults aged 40-70 years. 2. Diagnosis of type 2 diabetes within the previous 8 years using criteria of the American Diabetes Association 3. Currently treated with no hypoglycemic agents other than a stable dose (>3 months) of metformin (≥ 1.0 to ≤ 2 grams daily). 4. HbA1C between 6 to 9% (both inclusive) 5. BMI 25 to 39.9 kg/m² (both inclusive)

Exclusion Criteria:	
Patients with:
 
 1. Contraindications for moderate exercise 2. Implanted devices (e.g., pacemakers) that may interact with Tanita scale 3. Previous coronary or cerebrovascular event within 6 months of screening or active or clinically significant coronary and/or peripheral vascular disease 4. Low hematocrit (< 28 UNITS). 5. Pre-existing liver disease and/or ALT and AST $>2.5 \times$ UNL 6. Kidney disease at levels defined by: serum creatinine levels ≥ 1.5 mg/dL for men, ≥ 1.4 mg/dL for women, estimated CrCl ≤ 50 mL/min 7. History of pancreatitis, or cancer (except basal cell carcinoma) 8. Statin use started (or dose change) in the last 3 months, 9. Use of oral or injectable anti-diabetic medication other than Metformin 10. Daily use of a consistent long-term steroid medication (oral, inhaled, injected) within the last 3 months 11. Systolic BP > 140 mmHg and Diastolic BP > 90 mmHg at screening visit. 12. Active wounds or recent surgery within 3 months. 13. Inflammatory disease, or chronic current use of anti-inflammatory drugs within the last 3 months. 14. triglycerides >400 mg/dL 15. untreated hyper/hypothyroidism 
Additionally, patients who are active smokers, patients who are pregnant, nursing women, and post-menopausal women who are on hormone replacement therapy will be excluded.
 
Patients on low dose oral contraceptives will be allowed to participate as these formulations contain lesser amount of estrogens.

----------------------------	---

Criteria for Evaluation: (Efficacy, safety, stopping rules, etc.)	Subjects will be screened at week -4, then evaluated for end points at weeks 0, 6 and 12. Study participation will be stopped for adverse effects at the discretion of the study investigator. Subjects may stop study participation at any time and for any reason.
Statistics:	The total sample size requested, accounting for attrition over the 12-week period, is 20 subjects per group or 40 subjects total. Sample size estimates were based on the effects of exercise on CD34+/KDR+ cells as described in the literature. The effect of a single session, as well as extended training, on healthy subjects or those with existing cardiovascular conditions appears to increase the CD34+/KDR+ cells. This will provide 73% power (see statistics section). A p-value of less than 0.05 will be considered statistically significant.

1 INTRODUCTION

Type 2 diabetes is a national epidemic ^{1,2} with significant macro and microvascular complications³. Insulin resistance in prediabetes and early and late diabetes are associated with endothelial dysfunction⁴.

A few studies indicate that EPCs can act as a suitable bio-marker ⁵⁻⁷ for monitoring cardiovascular morbidity. In this proposal we suggest that EPCs or CD34 positive cells can act as a suitable cellular biomarker for estimating and following endothelial dysfunction in early type 2 diabetes patients.

EPCs have been used as a regenerative tool in ischemic myocardium and diabetic wound healing ⁸⁻¹³. Endothelial dysfunction with associated inflammation may be a consequence of excess super-oxide presence in a setting of diabetes which is a pro-oxidative stress condition causing EPC dysfunction and senescence¹⁴. Therefore monitoring EPC number, function and gene expression may serve as a very useful cellular bio-marker for cardiovascular complications in early type 2 diabetes.

Though lifestyle modification has been proposed as a main stay for prevention and treatment of early type 2 diabetes, ^{2, 15-19} several new therapies for diabetes have been developed in recent years². Incretins and incretin mimetics appear to hold promise. Oral DPP-4 inhibitors have been shown to increase EPCs in patients with type 2 diabetes ²⁰ reportedly via SDF-1 alpha up-regulation. Interestingly, up-regulation of SDF-1 alpha and vascular endothelial growth factor (VEGF), both chemotactic factors increase mobilization and recruitment of EPCs in the face of acute ischemic injury for repair and regeneration.²¹⁻²⁴.

Several studies have shown positive effect of incretins (Glucagon like peptide, GLP-1) and incretin receptor agonists (GLP-1 receptor agonists) on cardiovascular risk factors in type 2 diabetes patients^{20,25} and even in patients with chronic heart failure and left ventricular dysfunction who do not have diabetes^{26,27}.

DPP-4 Inhibitors may have cardio-protective effects of their own, as they increase bio-availability of endogenous GLP-1. They improve blood flow and nitric oxide production in endothelium^{28, 29}. These are unique properties not demonstrated by other oral diabetes medications ²⁸. The mechanism underlying these effects may be mediated by increased nitric oxide bioavailability but is not completely known. It is possible that Saxagliptin, a member of DPP-4 inhibitor group of drugs may be able to improve number and function

of CD34+ endothelial progenitor cells by up-regulating chemotactic agent SDF1 alpha (DPP-4 degrades SDF-1) and its receptor CXCR4^{7, 20, 21, 30, 31}.

Poor viability and function of EPCs in early diabetes may ultimately affect the repair and regeneration of the endothelium and prompt intervention may reduce or reverse cardiovascular risk by improving EPC survival and function above and beyond adequate glucose metabolism control.

Therefore we would like to explore the effect of Saxagliptin in addition to lifestyle intervention, on number and function and gene expression of EPC and impact on endothelial dysfunction in type 2 diabetes.

This proposed study will recruit patients with type 2 diabetes of less than 8 years duration, who are already on Metformin (≥ 1.0 to ≤ 2 gm/d, stable dose for at least 3 months) but still remain poorly controlled with HbA1C between 6% and 9% (both values inclusive), but not overtly out of control ($> 9\%$ of HbA1C). In these patients we seek to compare the effect of saxagliptin and lifestyle modification versus lifestyle modification and placebo on endothelial function, particularly the cellular end-point. Initially life-style intervention with diet and regular aerobic activity (as per Standards of Diabetes Care: Diabetes Care Supplement: Jan 2014) will be undertaken for 4 weeks. Subjects will begin taking 5.0 mg of Saxagliptin or placebo after initial 4 weeks of stabilization of life style modification and will be withdrawn from the study if the medication or placebo is not tolerated. We will use the maximum approved dose of saxagliptin in order to discern a definitive effect.

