4.2.3 Discontinuation of Subjects from Treatment

Subjects MUST discontinue investigational product (and noninvestigational product at the discretion of the investigator) for any of the following reasons:

- Withdrawal of informed consent (subject's decision to withdraw for any reason).
- Any clinical adverse event, laboratory abnormality, or intercurrent illness which, in the opinion of the investigator, indicates that continued participation in the study is not in the best interest of the subject.
- Changes in estimated CrCL to ≤ 50 mL/min necessitating reduction in saxagliptin dose
- Treatment with systemic cytochrome P450 3A4 (CYP 3A4) inhibitors necessitating reduction in saxagliptin dose
- Pregnancy
 - Instruct WOCBP to contact the investigator or study staff immediately if they suspect they might be pregnant (e.g., missed or late menstrual period) at any time during study participation. Institutional policy and local regulations should determine the frequency of on-study pregnancy tests for WOCBP enrolled in the study.
 - The investigator must immediately notify BMS if a study subject becomes pregnant.
- Loss of ability to freely provide consent through imprisonment or involuntary incarceration for treatment of either a psychiatric or physical (e.g., infectious disease) illness.

All subjects who discontinue should comply with protocol-specified follow-up procedures outlined in Section 6. The only exception to this requirement is when a subject withdraws consent for all study procedures or loses the ability to consent freely (i.e., is imprisoned or involuntarily incarcerated for the treatment of either a psychiatric or physical illness). If a subject withdraws before completing the study, the reason for withdrawal must be documented appropriately.

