5.4.1 Dose Modifications

A single dosage adjustment to 2.5 mg daily is recommended for patients with moderate or severe renal impairment, or with end-stage renal disease ($\text{CrCl} \leq 50 \text{ mL/min}$, approximately corresponding to serum creatinine levels of $\geq 1.7 \text{ mg/dL}$ in men and $\geq 1.5 \text{ mg/dL}$ in women). Assessment of renal function is recommended before initiation of saxagliptin, and periodically thereafter. Given that this study protocol includes only saxagliptin 5 mg dose, the participation of any study subject requiring dose adjustment while on study medication will be discontinued (see section 4.2.3.).

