8 STATISTICAL CONSIDERATIONS

Statistical Analysis:

Sample Size Estimation:

The total sample size requested, accounting for attrition over the 12-week period, is 21 subjects per group or 42 subjects total.

Sample size estimates were based on the effects of exercise on CD34+/KDR+ cells and VEGF, as described in the literature⁴⁷⁻⁵⁰. The effect of a single session, as well as extended training, on healthy subjects or those with existing cardiovascular conditions appears to increase the CD34+/KDR+ cells and VEGF.

To compute sample size we used the approach suggested by Diggle, Liang, & Zeger (1994)⁵¹ which compares the rates of change in the two study groups over time. This approach incorporates the number and interval of time points and the correlation among repeated measures. For this study, we will employ one baseline and two follow-up measures at 6 and 12 weeks. Further, we will assume a correlation 0.60 among repeated measures of the outcome. [We consider this a conservative estimate since Frison and Pocock (1992)⁵² suggest a correlation of 0.65 as reasonable in the absence of an existing estimate. We also note that as this correlation increases, statistical power also increases.

The results in the table below show the expected mean difference in study groups at the end of follow-up, as well as the average rate of change in the two groups at 80% power and 90% power. To estimate the effect of saxagliptin on the CD34+/KDR+ cells, we expect that the effect would be at least 25% greater than the effect seen for exercise alone. Using the results from Sandri et al. (2005)⁴⁹ for the rate of change and the variability, the CD34+/KDR+ cells increased an average rate of about 4/wk with a standard deviation of about 15. Thus, for a 25% increase in the rate of change for the CD34+/KDR+ cells due to saxagliptin, a sample size of 18 subjects per group would provide about 84% power, assuming measures taken at baseline and 2 equally-spaced time points over 12 weeks. At the conclusion of follow-up, we would expect study groups to differ by an average of 12 cells. If the effect of saxagliptin is only 20%, a sample of 18 would provide about 70% power, whereas a sample of 20 would provide about 73% power.

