The distributional assumptions of all measures will be examined. Means and standard deviations will be computed for continuous measures and proportions for categorical variables. Graphical representations of the mean group slopes and individual slopes will be generated and inspected. Study groups will be compared to determine whether any imbalance between the groups on patient characteristics remain after randomization. If imbalance is evident, by inspection, all models will be adjusted for the unbalanced covariates. Change in outcome over time will be examined using a multilevel approach with linear mixed models (LMM)^{53,54}. The longitudinal multilevel modeling approach will enable us to examine characteristics of within-person change, as well as between-group differences that may influence change. LMMs handle missing data more efficiently than traditional ANOVA designs. In the linear mixed models, the patient is considered a random effect and the outcome measured at specific time points is nested within patient. In an initial model containing only the variable TIME, we will use a likelihood ratio test to determine whether a random effect for time should be modeled. The model below represents a random intercept for patient and a random coefficient for TIME.

$$Y_{ij} = \beta_0 + \beta_1 Time_{ij} + u_{i0} + u_{i1} Time_{ij} + \varepsilon_{ij}$$

We will examine whether TIME may be modeled linearly by testing the added contribution of TIME (represented with two indicator variables) to a model with TIME as a single continuous variable. Assuming time may be modeled as a continuous variable, subsequent analyses will add study group and other patient characteristics as covariates. We are particularly interested in whether there is a significant interaction between study group and time, adjusting for other patient level covariates. A significant interaction would indicate that the slopes in outcome over time differ by study group. If the global test of interaction is significant, subsequent significance testing of the pair wise comparisons of group slopes group will be adjusted for multiple comparisons. The model also includes coefficients for the group-by-time interactions and random effects for patient and time.

$$Y_{ij} = \beta_0 + \beta_1 Time_{ij} + \beta_2 Group_i + \beta_3 (Time_{ij} \times Group_i) + u_{i0} + u_{i1} Time_{ij} + \varepsilon_{ij}$$

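### The Introduction and synopsis end study participation for intolerance or adverse effects while Section 4.2.3 stops only study drug and keeps follow-up, so week 6 and 12 outcomes can be lost for treatment-related reasons

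*Combined protocol and SAP*

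**What the plan says.** Two places end participation in the study:

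- Introduction (Section 1): patients "will be withdrawn from the study if the medication or placebo is not tolerated".
- Protocol Synopsis, Criteria for Evaluation: "Study participation will be stopped for adverse effects at the discretion of the study investigator".

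Section 4.2.3 is written about drug. It opens with "Subjects MUST discontinue investigational product (and noninvestigational product at the discretion of the investigator) for any of the following reasons", and its list includes adverse events, a fall in creatinine clearance and CYP3A4 inhibitor treatment. It then says "All subjects who discontinue should comply with protocol-specified follow-up procedures outlined in Section 6", and limits the way out: "The only exception to this requirement is when a subject withdraws consent for all study procedures or loses the ability to consent freely".

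Sections 5.4.1 and 5.6.1 use participation wording as well ("the participation of any study subject requiring dose adjustment while on study medication will be discontinued"), but both refer the reader to 4.2.3.

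On the analysis side, Section 8 plans that "we will employ one baseline and two follow-up measures at 6 and 12 weeks". Its only remark on missing data is that "LMMs handle missing data more efficiently than traditional ANOVA designs". It names no analysis set, does not say how data collected after stopping drug are used, and gives no sensitivity analysis for missing data.

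**The concern.** A patient who stops for intolerance leaves the study under the Introduction but stays under follow-up in 4.2.3. A site cannot do both. If it follows the Introduction or the synopsis, the remaining outcome visits do not take place. The schedule in Section 6.2 has weeks -4, 0, 6 and 12 and no early-termination visit, so a patient removed before week 6 contributes only a baseline value.

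Such outcomes are missing because of how the patient fared on treatment, and the rate can differ between arms. The mixed model is valid under this kind of loss only if missingness depends on data already observed. With one baseline and at most one later value per removed patient, there is little observed data to carry that assumption. The comparison would drift from all randomised patients toward those who tolerate their tablets. Values not collected at weeks 6 and 12 cannot be recovered in the analysis.

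**Working it through.** **1. The passages side by side**

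| Event | Introduction / synopsis | Section 4.2.3 |
|---|---|---|
| Drug or placebo not tolerated | Withdrawn from the study | Not a named exception to follow-up |
| Adverse effect | Participation stopped, investigator's discretion | Stop investigational product; follow-up continues |
| Dose adjustment needed (5.4.1, 5.6.1) | Not addressed | Stop investigational product; follow-up continues |

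The first two rows conflict. In the third, 5.4.1 and 5.6.1 say that participation ends but point to 4.2.3, so the mismatch there is one of wording.

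**2. How many patients**

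Inputs are the pooled adverse-event discontinuation rates in Section 1.1.4.1 (3.3% on 5 mg, 1.8% on placebo) and 20 or 21 patients per arm, since Section 8 gives both.

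- 20 per arm: 20 × 0.033 = 0.66 and 20 × 0.018 = 0.36, together 1.02.
- 21 per arm: 21 × 0.033 = 0.69 and 21 × 0.018 = 0.38, together 1.07.
- Chance of at least one such stop in the trial: 1 − 0.967^20 × 0.982^20 = 64%, or 66% at 21 per arm.

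**3. Possible size of the bias**

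Assumption, not in the documents: a share f of the saxagliptin arm stops, has no excess slope and is removed, while the model still estimates the planned 12-cell difference. The difference in all randomised patients is then 12 × (1 − f), and the relative overstatement is f / (1 − f).

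| f | Difference, all randomised | Overstatement |
|---|---|---|
| 3.3% | 11.6 cells | 3% |
| 10% | 10.8 cells | 11% |
| 20% | 9.6 cells | 25% |

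**4. Does retention add power?**

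The plan's own figure comes first. For a comparison of slopes, power = Φ(d / √[2·SD²·(1 − ρ) / (n·Sxx)] − z). Section 8 gives SD 15, ρ 0.60 and d = 1 cell per week. Times 0, 6 and 12 give Sxx = 36 + 0 + 36 = 72. At n = 18 the standard error is √(2 × 225 × 0.4 / (18 × 72)) = 0.3727, and d/SE = 2.683. With one-sided 0.05 (z = 1.645) power is 85%, which matches the stated 84% within rounding. With two-sided 0.05 (z = 1.960) it is 76.5%. The sidedness is a separate matter; two-sided values are used below.

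- Full effect kept by everyone: 76.5% at 18, 80.7% at 20, 82.6% at 21 per arm.
- Patients off drug measured but with no excess slope (assumption): 20 per arm with 2 off drug, d = 18/20 = 0.90, gives 72.1%; 21 per arm with 3 off drug, d = 18/21 = 0.857, gives 70.0%.
- Patients off drug keeping half the effect (assumption): 76.6% and 76.8%.

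So measuring patients after they stop can raise or lower power. The break-even lies near half the effect retained.

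**The case against.** The best defence is that 4.2.3 is the detailed operative section, states its exceptions explicitly and calls them the only ones, whereas the Introduction is background text. The synopsis leaves adverse effects to the investigator's discretion, and the adverse-event item in 4.2.3 uses a similar test, itself phrased in terms of continuing in the study. This softens the synopsis conflict. It also shows that 4.2.3 does not separate stopping drug from leaving the study cleanly. The Introduction sentence has no such qualifier, and its conflict with 4.2.3 stands.

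Nor does 4.2.3 settle the matter through its reference to Section 6. The body numbers both Study Assessments and Procedures and Adverse Event Reporting as 6. The contents list points to the former, but a site could read the duty as safety follow-up only.

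Two stronger readings might be inferred, and neither is supported:

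- That 5.4.1 and 5.6.1 are further independent conflicts. Their reference to 4.2.3 sends the reader to the follow-up requirement, so it does not follow that outcome data would go uncollected.
- That keeping these patients lifts power from 76.5% to 80.7% or 82.6%. This treats all the planned attrition (2 of 20 or 3 of 21 per arm) as caused by this wording, although Section 8 budgets for attrition in general and the synopsis lets patients leave for any reason. It also assumes that patients off drug keep the full effect.

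**Conclusion.** The point holds as an inconsistency that can cause treatment-related loss of outcome data. It is clear for the Introduction against 4.2.3, softer for the synopsis, and a matter of wording alignment for 5.4.1 and 5.6.1.

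The expected size is small. About one adverse-event stop is expected in the whole trial, and the overstatement is about 3% if only 3.3% of the saxagliptin arm is affected. It would reach 11% at a 10% share and 25% at 20%. These figures assume that the pooled programme rates carry over to this 12-week trial and that patients who stop lose the whole excess slope; the documents establish neither. The case rests on bias and on keeping the comparison of all randomised patients, and it does not rest on power. It should be corrected because the loss cannot be repaired afterwards and the correction is cheap. Which clinical stopping rule is right is not judged here.

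**What to change.** Reconcile the Introduction, the synopsis and Sections 5.4.1 and 5.6.1 with 4.2.3 so that stopping study drug and leaving the study are separate events. Specifically:

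- State that patients off drug are asked to attend the already scheduled week 6 and week 12 outcome visits. Keep the exceptions already in 4.2.3 (consent withdrawn for all procedures, or loss of the ability to consent freely) and the limit in Section 6.5 on procedures contraindicated by pregnancy.
- State in Section 8 that their data enter the mixed model under the randomised arm.
- In 4.2.3, replace the bare section number with the title Study Assessments and Procedures.

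This concerns outcome collection only and leaves unchanged when drug is stopped. The cost is a few sentences of text and a few visits by patients no longer on drug, each with the 85 mL blood draw described under the secondary measures.
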